11.1. Adverse Events

All reported AEs will be coded according to MedDRA.

An Adverse Event (AE) is defined as treatment-emergent, if first onset or worsening is after start of the first infusion of *NewGam*. Only treatment-emergent AEs (TEAE) are accounted for in the analysis.

A TEAE will be considered to be temporally associated with the infusion (or 'infusional') if it starts during or within 72 hours of the end of the infusion.

All treatment-emergent AEs for each patient, including multiple occurrences of the same event, will be listed in full detail, including reported term, MedDRA preferred term and system organ class, onset, duration, time to the AE occurrence from last dose, causality, dosage, severity, seriousness and actions taken.

For each dose group and for the study as a whole the following will be given:

- Total number of TEAEs reported
- Number of temporally associated TEAEs
- Number and percentage of infusions temporally associated with one or more TEAE
- Number of temporally associated TEAEs divided by the total number of infusions

On a per patient basis the incidence of TEAEs will be summarized by system organ class, preferred term and maximum severity. If a patient experiences an adverse event more than once the event at the most severe occurrence will be considered. Patients will be included only once under each system organ class and only once in the overall totals under the most severe event occurrence.

TEAEs will be summarized by strongest relationship to study medication by system organ class and preferred term. If a patient experiences an adverse event more than once the event most related to study medication will be considered. Patients will be included only once under each system organ class and only once in the overall totals under the most related to study medication occurrence.

Incidences of TEAEs (given as the number and percentage of patients) will be summarized overall and for each dose group as follows:

- Any TEAE
- Any serious TEAE
- Any TEAE probably or possibly related to the trial drug
- Any severe TEAE
- Any withdrawal due to TEAE
- Any significant TEAE
- Any TEAE by MedDRA System Organ Class (SOC) and MedDRA Preferred Term (PT)

Significant AEs fulfill at least one of the following criteria:

- any concomitant medication or therapy started due to the AE
- Study treatment was stopped/withdrawn or dose changed

Narratives will be prepared describing each death, each other serious AE and those of the other significant AEs that are judged to be of special interest because of clinical importance .

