
 • Time to first confirmed worsening on the adjusted INCAT disability scale by at least 1 point from the value at baseline (Week 0) • Mean change from baseline (Week 0) to Termination Visit in 
 ○ grip strength of both hands (assessed by Martin Vigorimeter) ○ Inflammatory Rasch-built overall disability sum score (I-RODS using the concept of MCID-SE as recently reported; Appendix 1) and number of improvers ○ sum of the distal evoked amplitude of 4 right sided and 4 left sided motor nerves (peroneal, tibial, ulnar and median) ○ Pain Intensity Numeric Rating Scale (PI-NRS) • Time to first confirmed worsening on the I-RODS scale • Time to 1 point decrease (improvement of disability) in adjusted INCAT disability score • Time to decrease in I-RODS scores 
Exploratory
 
 • Mean change from baseline (Week 0) to Termination Visit in: 
 ○ modified Fatigue Severity Scale (FSS; 7-item scale from 0-21 points; see Appendix 2) ○ number of improvers by at least 4 points in the MRC sum score (according to the universal rule of minimal clinical important difference) ○ SF-36 Health Survey physical composite score (PCS), mental composite score (MCS) and their 8 health domains (see Appendix 3) ○ additional NCS analyses (e.g. individual nerve analysis) • Time to decrease in MRC sum score to or below baseline value after temporary improvement (increase) 
Safety (throughout the entire Wash-out and Dose-evaluation Phases):
 
 • Occurrence of all adverse events (AEs) • Short term tolerance parameters including vital signs • Physical/neurological examination • Laboratory parameters (hematology and clinical chemistry) and tests for viral safety 	
Summary of Study Procedures and Statistical Analysis Plan:	
Study Procedures:	
Disability will be assessed by the adjusted INCAT score and the I-RODS at each visit.	
Pain will be assessed by the PI-NRS at each visit.	
Impairment will be assessed by the grip strength at each visit, MRC sum score and the modified FSS (Fatigue Scale) at Screening, Week 0, Week 12 and Termination Visit.	
Quality of life (SF-36) will be measured at Screening, Week 0, Week 12, and at Termination Visit.	

Name of Sponsor/Company: Octapharma Pharmazeutika Produktionsges.m.b.H., 1100 Vienna, AT	

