Name of Investigational Product: NewGam	Protocol Identification Code: NGAM-08 (ProCID)
Name of Active Ingredient: Immunoglobulin Intravenous (human) 10%	Date of Final Protocol: 08-June-2018

Electrophysiological measurements (nerve conduction studies) will be done at Screening, Week 0, Week 12, and at Termination Visit.
 
Adverse events (AEs) and serious adverse events (SAEs) temporally associated with administration of IMP or saline solution will be collected throughout the entire study (starting with the Wash-out Phase for patients on IGIV) as well as pregnancies, drug overdose, interaction, medication error, lack of efficacy, and post-study SAEs.
 
Laboratory safety tests (hematology and clinical chemistry) will be determined from blood samples taken at each visit. IgG level will be determined at each visit but Screening; viral markers will be determined at Screening, Week 0, and Termination Visit. Urinalysis will be performed at Screening and Termination Visit.
 
Statistical Analysis:
 
The primary endpoint will be evaluated by comparing the lower limit of the 95% Wilson-Score confidence interval for the percentage of responders on the adjusted INCAT disability scale in the 1.0 g/kg dose group with a predefined threshold of 42%.
 
The response rates in the alternative dose groups will be compared descriptively to the 1.0 g/kg treatment group, and the confidence intervals for the differences will be presented. In addition, an exploratory logistic regression, that includes the pre-treatment as well as the dose group as predictor variables, will be conducted. The same model will also be used for secondary response variables (based on grip strength, or I-RODS scores).
 
All other endpoints will be analyzed and presented in full detail by means of descriptive statistics, including summary and frequency tables, confidence intervals and graphs.
 
A formal statistical analysis plan describing all details of the analyses to be performed will be prepared by the study statistician and approved by the Sponsor prior to unblinding and the start of the statistical analysis.
 
The analysis of safety will be based on the safety set which includes all patients who received any study drug. The primary evaluation of efficacy endpoints will be based on the Full Analysis Set (intention-to-treat analysis).
	

The study assessments and scheduled time points are summarized in the Flowchart overleaf:

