FLOWCHART

	Screening	Wash-out Phase ¹	Dose-evaluation Phase ²								
	Visit 1 Week -15	Week -12 to 0	Visit 2 Week 0	Visit 3 Week 3	Visit 4 Week 6	Visit 5 Week 9	Visit 6 Week 12	Visit 7 Week 15	Visit 8 Week 18	Visit 9 Week 21	Termination visit Week 24
Informed consent	X										
Medical history	X										
In-/Exclusion criteria	X		X								
Randomization/Enrollment			X								
Concomitant medication		X ¹⁰	X	X	X	X	X	X	X	X	X
Adverse events		X ¹⁰	X	X	X	X	X	X	X	X	X
Physical/neurological examination	X		X				X				X
ECG	X										
Clinical chemistry ³ ; Hematology ⁴	X		X	X	X	X	X	X	X	X	X
Serum IgG ⁵			X	X	X	X	X	X	X	X	X
Urinalysis ⁶	X										X
Pregnancy test ¹¹	X										
Viral marker ⁷	X		X								X
PGIC scale			X								
Adjusted INCAT score; I-RODS score, PI-NRS	X		X	X	X	X	X	X	X	X	X
Grip strength	X		X	X	X	X	X	X	X	X	X
MRC sum score	X		X				X				X
Modified FSS	X		X				X				X
Nerve Conduction Studies	X		X				X				X
SF-36 Health Survey	X		X				X				X
Vital signs ⁸ ; Weight	X		X	X	X	X	X	X	X	X	
Study drug infusion			X ⁹	X	X, [X ^{12,13}]	X, [X ^{12,13}]	X, [X ¹²]	X, [X ¹²]	X, [X ¹²]	X, [X ¹²]	

¹ May last up to 12 weeks (until deterioration): Selection of active patients requiring treatment after dosage reduction

² Infusion visits take 2 days

³ Clinical chemistry: Na⁺, K⁺, glucose, ALAT/ALT/GPT, ASAT/AST/GOT, LDH, total bilirubin, BUN (blood urea nitrogen) or urea, creatinine, albumin, serum IgG

⁴ Hematology: Hematocrit, hemoglobin, CBC with differential

⁵ Serum IgG to be determined prior to infusion

⁶ Urinalysis: Protein, pH, glucose, ketones, leukocytes, hemoglobin and blood

⁷ Viral Markers: HIV, HBV and HCV

⁸ Vital signs: Pulse, blood pressure, respiratory rate and temperature

⁹ Loading dose of 2.0 g/kg NewGam

¹⁰ Only for patients on immunoglobulin treatment visiting the site for infusions

¹¹ Pregnancy test should only be done in women of childbearing potential (WOCBP). Pregnancy test is mandatory at Visit 1. At Visit 2, 3, 4, 5, 6, 7, 8, 9 and Termination Visit a pregnancy test should be performed only if required by local regulations.

¹² Two consecutive 3-weekly infusions of 2.0 g/kg NewGam only for patients on 0.5 or 1.0 g/kg NewGam who deteriorate after Week 3 and until Week 18

¹³ Two consecutive 3-weekly infusions of 2.0 g/kg NewGam only for patients on 0.5 or 1.0 g/kg NewGam being stable by Week 6

Signature of the Coordinating Investigator

This study is intended to be conducted in compliance with the protocol,

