3.1.2 Secondary Endpoints

Efficacy:

- Proportion of responders in the 0.5 g/kg and 2.0 g/kg NewGam arms at Week 24 relative to baseline at Week 0 compared to the 1.0 g/kg arm, based on the adjusted INCAT disability score
- Proportion of responders in the 0.5 g/kg and 2.0 g/kg NewGam arms at Week 24 relative to baseline at Week 0 compared to the 1.0 g/kg arm, based on the grip strength (Martin Vigorimeter) using the previously published minimum clinically important difference (MCID) cut-off of 8 kPa.[26]
- Proportion of responders in the 0.5 g/kg and 2.0 g/kg NewGam arms at Week 24 relative to baseline at Week 0 compared to the 1.0 g/kg arm, based on the I-RODS scores using the MCID concept related to the varying standard errors (MCID-SE) as recently demonstrated.[27]
- Time to first confirmed worsening on the adjusted INCAT disability scale by at least 1 point from the value at Baseline
- Mean change from Baseline (Week 0) to Termination Visit in
 - grip strength of both hands (assessed by Martin Vigorimeter) Inflammatory Rasch-built Overall Disability Sum Score (I-RODS using the concept of MCID-SE as recently reported; [Appendix 1](#)) and number of improvers
 - sum of the distal evoked amplitude of 4 right sided and 4 left sided motor nerves (peroneal, tibial, ulnar and median)
 - Pain Intensity Numeric Rating Scale (PI-NRS)
- Time to first confirmed worsening on the I-RODS scale
- Time to 1 point decrease (improvement of disability) in adjusted INCAT disability score
- Time to decrease in I-RODS scores

¹ The adjusted INCAT score is identical to the original INCAT disability score with the exception that upper extremity score changes from 0 (normal) to 1 (minor symptoms) or from 1 to 0 are excluded in determining the adjusted score, given that these changes are not considered clinically meaningful.

Safety:

Throughout the entire 24-week Dose-evaluation Phase:

- Occurrence of all adverse events (AEs)
- Short term tolerance parameters including vital signs
- Physical/neurological examination
- Laboratory parameters (hematology and clinical chemistry) and tests for viral safety
- Standard ECG (only at screening visit)

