6.1.2 Procedures During the Wash-out Phase of the Study

Eligible patients will have to enter a Wash-out Phase of up to 12 weeks, i.e., they have to decrease their current medication (immunoglobulins or corticosteroids; see Section 3.2). In this Phase the medication will successively be reduced until the patient deteriorates.

For patients on corticosteroids, no scheduled or required study evaluations/visits will take place during the Wash-out Phase. However the patients must inform the investigator whenever they notice any symptom of disease worsening at any time during the Wash-out Phase and must come to the site for assessment of deterioration. If deterioration cannot be confirmed, the Wash-out Phase will continue.

Patients on immunoglobulin treatment will have to visit the study site (e.g. IGIV every three weeks) for their infusions. Thus, from these patients concomitant medications and AEs will be recorded.

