9.2.3.1 Adverse Events

All reported AEs will be coded according to Medical Dictionary for Regulatory Activities (MedDRA).

An AE is defined as treatment-emergent, if first onset or worsening is after start of the first IMP administration. Only TEAEs are accounted for in the analysis.

A TEAE will be considered to be temporally associated with the infusion (or ‘infusional’) if it starts during or within 72 hours of the end of the infusion.

Incidences of TEAEs will be given as numbers and percentages of patients and infusions with:

- Any TEAE
- Any serious TEAE
- Any TEAE probably or possibly related to the trial drug
- Any severe TEAE
- Number of infusional TEAEs
- Number and percentage of infusions temporally associated with one or more TEAE
- Any withdrawal due to TEAE
- Any significant TEAE (see Section 7.3.1.1)
- Any TEAE by MedDRA Preferred Term (PT)
- Any TEAE by MedDRA System Organ Class (SOC)

Summary tables for TEAEs will be given by System Organ Class (SOC) and Preferred Term (PT). Additionally, TEAEs will be summarized by severity and relationship to study treatment.

All TEAEs for each patient, including multiple occurrences of the same event, will be listed in full detail, including reported term, MedDRA PT and SOC, onset, duration, time to the AE occurrence from last dose, causality, dosage, severity, seriousness and actions taken.

Narratives will be prepared describing each death, other SAEs, and other significant TEAEs that are judged to be of special interest because of clinical importance.

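### The stated safety period differs between the synopsis and the body of the plan, and adverse events recorded during the Wash-out Phase have no planned table or listing

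*SAP*

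**What the plan says.** **Period of the safety endpoints.** The protocol synopsis introduces them with "Safety (throughout the entire Wash-out and Dose-evaluation Phases" and lists the occurrence of all AEs first. Protocol 3.1.2 introduces the same endpoints with "Throughout the entire 24-week Dose-evaluation Phase", and SAP 3.2.2 follows 3.1.2.

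**Collection during wash-out.** The synopsis says that AEs "will be collected throughout the entire study (starting with the Wash-out Phase for patients on IGIV" treatment. Footnote 10 of the flowchart marks the wash-out AE and concomitant-medication cells "Only for patients on immunoglobulin treatment visiting the site for infusions". Protocol 6.1.2 explains that immunoglobulin patients come to the site for their infusions and continues: "Thus, from these patients concomitant medications and AEs will be recorded". For the other stratum it states: "For patients on corticosteroids, no scheduled or required study evaluations/visits will take place during the Wash-out Phase". Corticosteroid patients must, however, report any worsening and attend to have it assessed.

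**Analysis.** Protocol 9.2.3.1 says "Only TEAEs are accounted for in the analysis", and SAP 11.1 says "Only treatment-emergent AEs (TEAE) are accounted for in the analysis". In both, a treatment-emergent AE (TEAE) is one that starts or worsens after the first infusion has begun. The full-detail AE listing is also confined to TEAEs. SAP 11 presents safety for the safety set, which SAP 7 limits to patients who were randomized and had at least some study drug infused.

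**The concern.** The wash-out is something the study does to patients. Under protocol 3.2 and 6.1.2, therapy on which they depend (inclusion criterion 2) is reduced until they worsen, or for 12 weeks at most. A reader of the synopsis would expect the report to show which AEs occurred in that time. Sites are told to collect them for one of the two randomization strata, yet the analysis rules give them nowhere to go.

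Two things are at stake: whether the safety endpoint, as the synopsis states it, can be reported at all, and whether AEs in patients who were tapered and then not randomized are visible anywhere in the safety output.

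**Working it through.** The plan gives no figure to reproduce. The check follows a wash-out AE from collection to output; the only arithmetic concerns phase lengths.

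1. **Is it within the endpoint?** Yes under the synopsis; no under protocol 3.1.2 and SAP 3.2.2. These cannot all stand.

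2. **Is it collected?**
   - Immunoglobulin patients: yes, at infusion attendances (synopsis, footnote 10, 6.1.2).
   - Corticosteroid patients: no visit is scheduled. If they attend because they feel worse, protocol 7.3.1.2 has AEs elicited at every visit, planned or not, whereas footnote 10 confines wash-out collection to the other stratum. The two rules conflict.
   - At Visit 2, protocol 6.1.3 places AE monitoring among the activities during and after infusion, so no question about the preceding weeks is specified before the first dose.
   - The AE definition in 7.3.1.1 refers to patients receiving study drug, which leaves the status of a wash-out event unclear.

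3. **Does it reach the AE tables or the AE listing?** An event that starts and ends in wash-out is not a TEAE, so under protocol 9.2.3.1 and SAP 11.1 it does not. There are two exceptions. An event that worsens after the first infusion becomes a TEAE. Under SAP 8.3, an event whose dates are too incomplete to place it before the infusion is presumed to be one.

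4. **Is the patient in the safety set?** Only if randomized and infused. Protocol 3.2 says that patients who do not deteriorate in wash-out are not enrolled, so their AEs fall outside every safety table whatever the TEAE rule says.

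5. **Is there another route to the report?**
   - Narratives (SAP 11.1): each death and each other serious AE, with no TEAE limit in the wording. A wash-out serious AE could appear here, but without a count or denominator.
   - Deterioration after wash-out (SAP 9.3): listed, and tabulated by dose group and by scale. This covers dosed patients only. Because deterioration is the condition for randomization, it describes how patients qualified; it does not report AEs.
   - Serious AE reporting (protocol 7.3.2): goes to the sponsor and is not a study output.

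6. **How long is the period?** From protocol 6.2.1: Screening about 3 weeks, wash-out up to 12, dose evaluation 24.
   - Check: 3 + 12 + 24 = 39 weeks, the stated maximum.
   - Share after Screening for a patient who uses both phases in full: 12 / (12 + 24) = 12 / 36 = 33%.
   - Wash-out ends at deterioration and can last anything above 0 weeks, so 12 weeks is a ceiling.

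**The case against.** The strongest defence is that the synopsis is the outlier. The secondary safety objective concerns NewGam administration, and protocol 3.1.2, SAP 3.2.2, the TEAE rule and the safety set all agree on reporting after the first infusion. The synopsis heading also covers laboratory tests and examinations that the flowchart does not schedule in wash-out, which suggests loose drafting. Narrowing the synopsis would remove the contradiction. That stands as far as it goes, but AEs that sites are required to record would still have no output, and the tapered, never-randomized patients would still be missing from the safety tables.

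It is also fair to say that the list of outputs is deferred to a separate document (SAP 2 and 13) and that patient data listings are foreseen, so a wash-out listing is not ruled out. None is specified, and the TEAE-only sentence points the other way.

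A reader might infer more than the documents support:

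- *All events before the first infusion are discarded.* No: see the two exceptions in step 3.
- *Nothing is collected from corticosteroid patients.* No: what is missing is scheduled wash-out collection. The general elicitation rule reaches unscheduled visits, though footnote 10 conflicts with it, and serious AEs must be reported.
- *Harm from withdrawal would be invisible.* No: deterioration is listed and tabulated for dosed patients, and serious events may be narrated.
- *The number of serious events lost can be estimated, or the 4% to 17% mortality in the protocol's introduction indicates the risk.* No: the documents give no wash-out event rate, and that figure is the share of CIDP patients who die from the disease, not a risk over at most 12 weeks of tapering.
- *The dose comparison is biased.* No: wash-out comes before randomization, which is stratified by prior treatment, so uneven capture between strata does not favour any dose group.

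**Conclusion.** The point holds as a reporting gap and a contradiction to be reconciled. The safety period is stated in two incompatible ways. Under the plan as written, wash-out AEs collected from immunoglobulin patients lack a planned AE table or listing, and capture in wash-out differs between the two strata. The effect is on the completeness of the safety report over a period of up to 12 weeks per patient; the dose-group safety tables and the efficacy analyses are untouched. The number of AEs involved cannot be derived from the documents. The conclusion assumes that the separate output document, which is not available here, adds no wash-out listing.

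**What to change.** **SAP 7 and 11.1.** Limit the TEAE-only sentence to the dose-group tables. Add a listing and a simple summary of AEs and serious AEs from the start of wash-out to the first NewGam infusion, by prior-treatment stratum, for all patients who entered wash-out, randomized or not. Add a note that capture differs between the strata.

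**Synopsis, protocol 3.1.2 and SAP 3.2.2.** State one safety period in all three.

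**Flowchart footnote 10 and protocol 6.1.2.** Reconcile them with 7.3.1.2, so that AEs are asked about in both strata at attendances that already take place: the assessment of deterioration, and Visit 2 before infusion. No new visit or contact is needed.

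**Cost.** A few extra outputs, the SAP part from data already collected. Data from corticosteroid patients will be incomplete and partly recalled. The collection changes help only patients not yet past wash-out. On the planned timetable (start in Q1 2017, about 20 months of enrollment) that may be few or none by the SAP date of 06-Jun-2019; the listing and summary remain feasible in any case.

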5.5 Dose and Dosing Schedule

NewGam is available in glass bottles with different volumes of human immunoglobulin. Glass bottles of different content should be combined in order to reach the required amount of IgG (split into infusions of 0.5 g/kg and 1.0 g/kg to maintain blinding). The total amount per patient should be dosed exactly. Partially used bottles must be discarded.

All patients should be clinically assessed for being adequately hydrated prior to infusion.

In the Dose-evaluation Phase, all patients will receive a loading dose of 2.0 g/kg Newgam (administered over two consecutive days), followed by seven infusions of the maintenance dose the patient has been randomized to (0.5, 1.0 or 2.0 g/kg NewGam), also administered over two consecutive days every 3 weeks (± 4 days). If a patient is randomized to receive the low or medium NewGam dose, the same volume with the same infusion rate as would have been applied in case the patient would have been randomized to 2.0 g/kg NewGam will be used, thus

supplemented with an authorized 0.9% w/v isotonic sodium chloride solution as appropriate and detailed in the following infusion bag split to maintain the blinding:

Treatment Arms	Infusion Bag Content	
	Day 1	Day 2*
0.5 g/kg NewGam	0.5 g/kg NewGam + 0.5 g/kg saline	1.0 g/kg saline
1.0 g/kg NewGam	0.5 g/kg NewGam + 0.5 g/kg NewGam	1.0 g/kg saline
2.0 g/kg NewGam	0.5 g/kg NewGam + 0.5 g/kg NewGam	1.0 g/kg NewGam

* Volume of Day 2 may be split up using 2 bags

The following infusion schedule must be adhered to in the Dose-evaluation Phase [all doses per kg body weight; rescue treatment only for patients who had been on 0.5 or 1.0 g/kg NewGam before, patients on 2.0 g/kg before will drop-out]:

1. Patients deteriorating* after Week 3 and before Week 6 or being stable at Week 6**

Week 0	Week 3	Week 6	Week 9	Week 12
2.0 g (LD)	0.5g 1.0 g	2.0 g (RT)	2.0 g (RT)	EOS
	2.0 g	EOS		

2. Patients deteriorating* after Week 6 and before Week 9

Week 0	Week 3	Week 6	Week 9	Week 12	Week 15
2.0 g (LD)	0.5g 1.0 g	0.5g 1.0 g	2.0 g (RT)	2.0 g (RT)	EOS
	2.0 g	2.0 g	EOS		

3. Patients deteriorating* after Week 9 and before Week 12

Week 0	Week 3	Week 6	Week 9	Week 12	Week 15	Week 18
2.0 g (LD)	0.5g 1.0 g	0.5g 1.0 g	0.5g 1.0 g	2.0 g (RT)	2.0 g (RT)	EOS
	2.0 g	2.0 g	2.0 g	EOS		

4. Patients deteriorating* after Week 12 and before Week 15

Week 0	Week 3	Week 6	Week 9	Week 12	Week 15	Week 18	Week 21

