2.0 g (LD)	0.5g 1.0 g	0.5g 1.0 g	0.5g 1.0 g	0.5g 1.0 g	2.0 g (RT)	2.0 g (RT)	EOS
	2.0 g	2.0 g	2.0 g	2.0 g	EOS		

5. Patients deteriorating* after Week 15 and before Week 18

Week 0	Week 3	Week 6	Week 9	Week 12	Week 15	Week 18	Week 21	Week 24
2.0 g (LD)	0.5g 1.0 g	0.5g 1.0 g	0.5g 1.0 g	0.5g 1.0 g	0.5g 1.0 g	2.0 g (RT)	2.0 g (RT)	EOS
	2.0 g	2.0 g	2.0 g	2.0 g	2.0 g	EOS		

LD – Loading Dose, RT – Rescue Treatment, EOS – End-of-Study-Visit

* = adjusted INCAT disability score increase of at least 1 point

** = adjusted INCAT disability score remains unchanged

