9.2 Statistical Analysis

A formal statistical analysis plan describing all details of the analyses to be performed will be prepared by the study statistician and approved by the Sponsor prior to unblinding and the start of the statistical analysis.

Data tabulations will comprise the results for the different dose groups and for the whole analysis set whenever appropriate. Evaluation of primary and secondary endpoints will be presented for each randomization stratum (prior treatment with Immunoglobulins or Corticosteroids) separately to facilitate the identification of noteworthy differences in the clinical responses between these two groups. No further subgroup analyses are pre-specified for this study, but the different CIDP variants eligible for enrollment, such as Multifocal Acquired Demyelinating Sensory And Motor Neuropathy (MADSAM) or pure motor CIDP, will be compared with respect to dose group, INCAT score and proportion of response as well. If indicated by the data, further comparisons between these CIDP variants will be added post-hoc.

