4.1. Overall Study Design and Plan

Study NGAM-08 is designed as a prospective, double-blind, randomized, multicenter phase III study. The rationale for conducting this study is to confirm the published clinical results obtained with the 1.0 g/kg dosing in order to apply for market authorization of NewGam, and to evaluate different dosing options on both sides of the standard dose with respect to efficacy and safety.

Patients will be screened for eligibility and, if eligible, thereafter have to decrease their current medication (Immunoglobulins by 25% from infusion to infusion or corticosteroids as per the discretion of the Investigator at a rate to expect study entry within 6-12 weeks) for a maximum of 12 weeks (Wash-out Phase). Only patients who deteriorate in this phase, i.e. active patients who need treatment, will be randomized 1:2:1 between three different dosages of NewGam (0.5 g/kg, 1.0 g/kg or 2.0 g/kg NewGam), and enter the Dose-Evaluation Phase.

[figure not shown]
The two allowed types of treatment prior to enrollment – Immunoglobulins or Corticosteroids – will be considered as strata in a stratified block design randomization with fixed block size. An electronic IWRS tool will be used to realize the randomization ratio of 1:2:1 with respect to the dosage groups, in each of the strata independently.

During the 24-week Dose-evaluation Phase all patients will first receive an initial loading dose of 2.0 g/kg NewGam, followed by 7 maintenance dosages of 0.5 g/kg, 1.0 g/kg or 2.0 g/kg NewGam every 3 weeks as they were randomized to.

Patients not deteriorating in the 12-week Wash-out Phase will not be enrolled into the ProCID study as they are not having active CIDP.

In addition the following rescue treatment option will be available: two consecutive infusions of 2.0 g/kg NewGam at 3-week intervals for all patients in the 0.5 and 1.0 g/kg NewGam arms who are either stable at Week 6 or deteriorate after Week 3 and before Week 18. Patients in the 2.0 g/kg NewGam arm will drop-out if they are stable at Week 6 or deteriorating after Week 3 and before Week 21.

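### SAP 11.1 splits TEAE summaries, including infusion-level rates, only by dose group and overall, so on the natural reading 2.0 g/kg loading and rescue infusions fall in the 0.5 and 1.0 g/kg columns

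*SAP*

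**What the plan says.** SAP 11.1 counts TEAEs from the first NewGam infusion. It sets the columns for total TEAEs, temporally associated TEAEs and infusion-level rates with "For each dose group and for the study as a whole the following will be given". One of those rates is "Number of temporally associated TEAEs divided by the total number of infusions". Patient-level results have the same columns: "Incidences of TEAEs (given as the number and percentage of patients) will be summarized overall and for each dose group as follows". Protocol 9.2 sets the same general split: "Data tabulations will comprise the results for the different dose groups and for the whole analysis set whenever appropriate".

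Every arm starts with a 2.0 g/kg loading dose, followed by seven maintenance infusions at the randomized dose (SAP 4.1, Protocol 5.5). SAP 4.1 also offers rescue: "two consecutive infusions of 2.0 g/kg NewGam at 3-week intervals for all patients in the 0.5 and 1.0 g/kg NewGam arms". Protocol 5.5 sets out five rescue paths. The earliest is for patients deteriorating "after Week 3 and before Week 6 or being stable at Week 6", with rescue at Weeks 6 and 9. The latest is for those deteriorating "after Week 15 and before Week 18", with rescue at Weeks 18 and 21. The 2.0 g/kg arm has no rescue; its patients leave the study instead.

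Protocol 9.2.3.1 heads its TEAE list "Incidences of TEAEs will be given as numbers and percentages of patients and infusions with". SAP 11.1 gives serious, severe and related TEAEs per patient only. In SAP 11.1 the dose is tied to an event only in the TEAE listing.

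**The concern.** Safety at the various dosages is a secondary objective (SAP 3.1.2). Protocol 3.2 says the maintenance dosages will be compared on safety, and Protocol 1.2 names lower adverse-effect risk at a lower dose as a possible benefit of the trial. A reader of an infusion-level rate in the 0.5 g/kg column may take it as the rate after a 0.5 g/kg infusion. Part of its denominator, and possibly a larger part of its events, would come from 2.0 g/kg infusions. The loading dose is common to all arms and dilutes infusion-level contrasts. Rescue adds 2.0 g/kg exposure to the two lower arms only. If risk rises with the dose infused, which the documents do not quantify, the gap to the 2.0 g/kg arm could look smaller than it is.

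**Working it through.** The documents give no TEAE rate and no expected rescue rate, so there is no plan figure to reproduce. The check is a count from the dosing schedule, followed by algebra.

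**Inputs.** Schedule: Protocol 5.5. Arm sizes: 140 patients at 1:2:1, so 140/4 = 35, 70 and 35. Assumptions: one infusion is one two-day infusion visit, follow-up is complete apart from the scheduled rescue exits, and 20% to 40% of an arm is rescued.

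**Infusion visits per patient, 0.5 and 1.0 g/kg arms**

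| Path | All visits | At 2.0 g/kg | Share |
|---|---|---|---|
| No rescue | 8 | 1 | 12.5% |
| Rescue from Week 6 | 4 | 3 | 75% |
| Rescue from Week 9 | 5 | 3 | 60% |
| Rescue from Week 12 | 6 | 3 | 50% |
| Rescue from Week 15 | 7 | 3 | 42.9% |
| Rescue from Week 18 | 8 | 3 | 37.5% |

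Without any rescue, the 0.5 g/kg column holds 35 × 8 = 280 visits, 35 of them at 2.0 g/kg. The 1.0 g/kg column holds 70 × 8 = 560, with 70 at 2.0 g/kg.

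**Arm-level share s, with fraction f rescued.** The numerator per patient is (1 − f) × 1 + f × 3. The denominator is (1 − f) × 8 + f × 4 if all rescue starts at Week 6, and 8 if all starts at Week 18.

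- Week 6: f = 0.2 gives 1.4/7.2 = 19.4%; f = 0.4 gives 1.8/6.4 = 28.1%.
- Week 18: f = 0.2 gives 1.4/8 = 17.5%; f = 0.4 gives 1.8/8 = 22.5%.

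**Effect if per-infusion risk depends only on dose infused.** Let p2 be the risk at 2.0 g/kg and pL the risk at the lower dose. The lower-dose column shows s × p2 + (1 − s) × pL, and the 2.0 g/kg column shows p2. The difference shown is (1 − s) × (p2 − pL), so the part kept is 1 − s whatever the two risks are:

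- no rescue: 87.5%
- Week 18 rescue: 82.5% (f = 0.2) and 77.5% (f = 0.4)
- Week 6 rescue: 80.6% (f = 0.2) and 71.9% (f = 0.4)

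**Effect if infusion order also matters.** Assume that 40% of each arm meets the Week 6 rule, that risk is 40% at the first infusion in every arm, and that later infusions carry 10% at 2.0 g/kg and 8% at the lower dose.

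- 2.0 g/kg arm: 0.6 × 8 + 0.4 × 2 = 5.6 visits per patient, 4.6 after the first. Rate = (0.4 + 4.6 × 0.1)/5.6 = 15.4%.
- Lower arm: 6.4 visits per patient, of which 1 is loading, 0.8 rescue and 4.6 maintenance. Rate = (0.4 + 0.8 × 0.1 + 4.6 × 0.08)/6.4 = 13.3% (13.25%).

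The difference shown is 2.1 points against a true 2.0, so nothing is lost. With a 30% first-infusion risk the rates are 0.76/5.6 = 13.57% and 0.748/6.4 = 11.69%, a difference of 1.88 points, or 94% of the true one. The 2.0 g/kg arm gives more weight to first infusions because its patients who are stable at Week 6 leave after 2 infusions.

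**What counts as an infusion.** Under the bag split in Protocol 5.5, Day 2 of every 0.5 or 1.0 g/kg maintenance visit is saline only. Counted by day, a patient without rescue in either lower arm has 16 infusion days, 7 of them saline only. The SAP does not say which unit it uses.

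**The case against.** The strongest reply is that the by-arm tables already answer the stated question. Protocol 3.2 compares dosing schemes, the loading dose belongs to every scheme, and the randomized comparison is the one by arm. Safety by dose infused is a different, non-randomized question, and neither document promises summary tables for it. This stands, and it is why the by-arm tables should remain the main ones.

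The exposure mix is also not hidden. SAP 9.4 lists and summarizes the actual dose per kg and the number of infusions, SAP 10.2 tabulates deteriorations by dose group and by whether they led to rescue, and the TEAE listing carries dosage and time from last dose. These let a reader see the mix in a column, but they do not give an event rate by dose infused.

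Four stronger readings are tempting, and the documents do not support them:

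- A reader might infer that the SAP expressly places rescue infusions in the lower-dose columns. It does not. The as-randomized sentence in SAP 7 belongs to the full analysis set, and no assignment rule is given for the safety set. The reading is natural because SAP 10.1 still reports response after rescue by dose group, but the table list is deferred (SAP 2 and 13) and may add a split.
- A reader might infer that the dose contrast must be attenuated whenever risk rises with dose. That needs risk to depend on dose alone. Protocol 1.2 names infusion rate and lack of prior IGIV exposure as further drivers, patients treated with corticosteroids are eligible (Protocol 4.1.1), and Protocol 5.6 allows a faster step-up from the third infusion.
- A reader might infer from SAP 8.4, which leaves out values under rescue when calculating changes in efficacy scores, that safety must be split too. It need not be: counting all on-study events is a coherent safety rule.
- A reader might infer that Protocol 9.2.3.1 requires a per-infusion figure for every row. Its heading covers patients and infusions, but the list has its own infusion item and includes withdrawals, where a per-infusion rate means little. The scope is ambiguous.

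**Conclusion.** The gap is real and small. As written, SAP 11.1 offers no summary of TEAEs by dose infused, and on the natural reading 12.5% of infusion visits in the lower-dose columns are at 2.0 g/kg without rescue. With 20% to 40% rescued (assumed) the share is 17.5% to 28.1%, and for an individual rescued patient it is 37.5% to 75%. These shares rest on the Protocol 5.5 schedule and on counting two-day visits.

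The retained differences, 87.5% without rescue and about 72% to 83% with rescue, hold only if per-infusion risk depends on dose infused and nothing else. They show what could happen and are not a forecast. If risk does not rise with dose there is nothing to attenuate, and if order, prior exposure or rate also matter, the distortion can be smaller or absent. The by-arm tables remain valid for assigned regimens, and the primary endpoint and sample size are untouched. This is a cheap improvement to consider before unblinding.

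**What to change.** Keep the by-arm TEAE tables as the main ones. In SAP 11.1:

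1. Define one infusion as one two-day infusion visit, so that saline-only days or bags do not enter the denominators.
2. State that dose group in the safety set means the randomized arm, if that is intended.
3. Add supplementary infusion-level tables of temporally associated (72-hour) TEAEs by phase and dose infused, in five unpooled columns: loading 2.0; maintenance 0.5, 1.0 and 2.0; rescue 2.0 g/kg. Use the number of infusions in each column as denominator.
4. Add related and severe TEAEs per infusion, in line with the heading of Protocol 9.2.3.1. Show serious TEAEs as counts, since they will be sparse.
5. Footnote that comparisons across phases are not randomized and are confounded with infusion order, disease state and infusion rate. The rescue column holds only patients who were stable or worse.

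The cost is a few extra descriptive tables from data already recorded (dose per infusion, event onset, time from last dose). No new data are needed and no other analysis changes. The downside is that the phase columns could be over-read, which the footnote addresses.
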